2.4 Rationale

Surgical resection continues to be the only hope for cure from pancreatic cancer, however, only 10-15% of patients present with resectable disease and those with negative surgical margins tend to have a favorable prognosis (64). Therefore, employing strategies to increase the proportion of resectable or borderline resectable pancreatic cancer patients who are able to undergo surgery with negative margins is of great importance.

Immune checkpoint blockade, including PD-1/PD-L1 and/or CTLA-4 inhibition, has yielded disappointing results in advanced pancreatic cancer (65, 66), and our experience in the neoadjuvant setting also suggests limited activity of PD-1 inhibition(67). Thus, there is a crucial need to test novel immunomodulatory approaches to altering the pancreatic tumor microenvironment and improving clinical outcomes.

In this trial, we will evaluate the effect of adding NIS793 to standard of care neoadjuvant mFOLFIRINOX, with or without radiation. mFOLFIRINOX is routinely administered at our institution as neoadjuvant treatment for resectable or borderline resectable pancreatic cancer. We anticipate that the immunomodulatory effects of TGF β blockade (Section 1.1) will synergize with the pro-inflammatory, anti-tumor effects of mFOLFIRINOX (Section 1.1) in the tumor microenvironment. We hypothesize that this synergy will lead to improved major pathological response rate, the primary outcome of our study, as well as progression-free and overall survival.

NIS793 is being evaluated in the metastatic setting and as of 18-May-2021, there have been no dose limiting toxicities in 120 patients that received treatment as single agent or in combination with PD-1 inhibition. This supports the safety profile of this agent and the incorporation of NIS793 in the neoadjuvant setting, in combination with standard therapy.

The utilization of this regimen in the neoadjuvant setting will also allow for extensive correlative studies that will contribute to our understanding of the pancreatic TIME and inform future translational and clinical studies.

2.5 Correlative Studies Background

Neoadjuvant trials are exceptionally positioned to explore the biological and immunological effects of systemic cancer therapies. In this trial, we will collect biospecimens to elucidate the effect of combination immunotherapeutic agents with FOLFIRINOX on pancreatic cancer, the pancreatic cancer microenvironment, and systemic changes that are reflected in peripheral blood. These specimens will include pancreatic cancer tissue from the surgical resection or biopsy taken during attempted resection; peripheral blood, plasma and additional specimens.

To determine the additive effect of NIS793 beyond FOLFIRINOX, we plan to perform several correlative studies. Based on the preclinical data presented above, we hypothesize that NIS793 will lead to increased CD8 T-cell infiltration into the pancreatic tumor microenvironment, with expansion of tumor-associated T-cells in the tumor and peripheral blood. To test this hypothesis, we will enumerate CD8+ and CD8+CD45RO+ cells within and around the tumor and characterize the distributions of T-cells relative to intratumoral stroma. We will also sequence the unique T-cell receptors that are found in the tumor and peripheral blood, and compare clonal overlap.

We also hypothesize that the distribution of fibroblasts will be altered with NIS793 treatment. The role of TGF-beta in stroma formation suggests that alterations of the stromal compartment would be expected as well. These will be assayed by using scRNA-seq and more focused targeted immunofluorescence panels. We will further characterize tumor cell transcriptional state via transcriptional profiling and multiplex immunofluorescent panels.

We also hypothesize that there are unanticipated changes that will occur in the microenvironment with NIS793 treatment, that could provide further insight into the drivers of histological and / or clinical outcome. We are therefore planning to take an unbiased approach and leverage single cell and bulk RNA sequencing to describe the cellular composition and the transcriptomic landscape of pancreatic cancer treated with NIS793. We will also compare the cellular composition and transcriptomic landscape of tumors treated with NIS793 vs those in the control arm. Furthermore given likely heterogeneity to response to therapy we will compare tumors treated with NIS793 based on the level of histologic response to therapy.

Finally, for our radiomics investigations, we plan to measure the baseline and post-neoadjuvant CT scans of patients as previously described (58-61). We will compare the delta classification with the measures of immune infiltration and peripheral blood assays, hypothesizing that the high delta tumors will exhibit more immunosuppression than the low delta tumors based on these assays. We also hypothesize that the interface response on CT will further stratify patients based on these immune-related endpoints. Clinical outcomes will be correlated with the CT-based radiomic features and Kaplan Meier curves will be constructed, along with appropriate univariable and multivariable analyses.

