cells in vivo to a classical cell state. This skewing was further exemplified by expression of the classical lineage marker Tff2 (Figure 5). Based on these data, we hypothesize that TGFB blockade with NIS793, a novel clinical grade anti-TGFB1/2 antibody, disrupts a critical trophic tumor cell-CAF signaling network to polarize tumor cells to a classical lineage and sensitize to chemotherapy.

Radiomics of PDAC

We have previously shown that quantitative imaging features of PDAC associate with the delivery of, response to, and outcome after gemcitabine-based therapy and radiation (58). These findings were further validated in retrospective datasets and prospective trial, focusing on a reproducible and visually apparent imaging feature prior to treatment termed the delta classification (59, 60). These studies demonstrate that patients with high delta PDAC demonstrate less stroma, more immunosuppressive elements in the TME, poorer responses to cytotoxic therapies, and worse survival outcomes, compared to those with low delta PDAC. Furthermore, we have identified a metric of response on conventional contrast-enhanced computed tomography (CT) scans that focuses on how the interface of the tumor changes during cytotoxic therapies. This interface response associated with pathological response to neoadjuvant therapy and survival outcomes of patients with resectable, borderline resectable, locally advanced, and metastatic PDAC in retrospective and prospective studies (59, 61). Here, we propose correlating these two imaging features of PDAC on CT scans with our immune-related measurements and the clinical outcomes in the two arms, hypothesizing that patients with high delta tumors and poor interface responses will exhibit differential responses to the experimental therapy, compared to low delta tumors.

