Given that mFOLFIRINOX is standard of care, study treatment will be continued as per institutional standard of care.

No pre-medications for mFOLFIRINOX are to be administered during the NIS793 observation window.

The FOLFIRINOX regimen will be administered intravenously. Treatment will be every 14 days +3/-1 days at physician discretion (unless a further delay is mandated by toxicity criteria). There will be eight cycles of FOLFIRINOX, with each cycle being 14 days in length. Treatment will be administered on an *outpatient* basis. Participants enrolled on Arm A will be treated with mFOLFIRINOX chemotherapy as per institutional standards with NIS793 at 2100mg IV every 2 weeks. Participants enrolled on Arm B will be treated with mFOLFIRINOX chemotherapy alone as per institutional standards.

Dosing schedules and modifications: all commercially supplied drugs will follow the manufacturer-provided labeling with respect to its storage and stability, preparation, handling, and administration. Decisions regarding dose modifications, and delays will be made for each patient at the discretion of the attending physician. All other treatments, including chemotherapy pre-medications, will be determined at the discretion of the attending physician.

All treatments, anti-emetics, and supportive medications should follow institutional guidelines. Subcutaneous growth factor support will be administered between 0 and 72 hours after

discontinuation of continuous infusion of 5-FU in all patients receiving FOLFIRINOX after each cycle. Participants may self-administer at home or have the injection administered in clinic.

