5.3.3 Restaging during/after FOLFIRINOX +/- NIS793

Participants will be restaged after four cycles of therapy (interim scans) and following the completion of induction mFOLFIRINOX (after eight cycles of therapy). Restaging scans can be performed after mFOLFIRINOX C4 and C8 pump disconnect (at the earliest) but must be completed prior to C5 and prior to RT administration, if the latter is required. The post-C4 scan review visit can be combined with the C5D1 visit pre-infusion. The post-C8 scan review can be combined with the pre-RT visit if RT is required. Up to one week's delay between cycles for restaging is allowed. Participants who do not demonstrate progression on either restaging scan will undergo RT and/or surgery depending on treatment arm.

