9.2.3 Serum cytokine analysis

We will evaluate the concentration of serum cytokines and chemokines using a multiplex panel including but not limited to the following analytes: 6CKine, BCA-1, CTACK, EGF, ENA-78, Eotaxin, Eotaxin-2, Eotaxin-3, FGF-2, Flt3L, Fractalkine, G-CSF, GM-CSF, GRO α , I-309, IFN α 2, IFN γ , IL-1 α , IL-1 β , IL-1RA, IL-2, IL-3, IL-4, IL-5, IL-6, IL-7, IL-8, IL-9, IL-10, IL-12p40, IL-12p70, IL-13, IL-15, IL-16, IL-17A, IL-17E/IL-25, IL-17F, IL-18, IL-20, IL-21, IL-22, IL-23, IL-27, IL-28A, IL-33, IP-10, LIF, MCP-1, MCP-2, MCP-3, MCP-4, M-CSF, MDC, MIG, MIP-1 α , MIP-1 β , MIP-1 δ , PDGF-AA, PDGF-AB/BB, RANTES, sCD40L, SCF, SDF-1 α + β , TARC, TGF α , TNF α , TNF β , TPO, TRAIL, TSLP, VEGF-A.

Serum will also be stored frozen for later in vitro analysis as needed.

This analysis will be performed in the [name] Lab at Dana-Farber Cancer Institute.

9.2.4 Circulating tumor DNA/Cell free DNA:

Circulating tumor DNA (ctDNA) is a sensitive molecular assay for tumor detection and evolution with therapy. We will use a sensitive quantitative circulating tumor DNA assay to assess early response or resistance to therapy. Early identification of tumor resistance to neoadjuvant therapy can allow later development of adaptive trials involving switching of chemotherapy backbone based on early response or resistance characterization. In addition, we will correlate single cell RNA profiles for tumors which demonstrate resistance vs. response to neoadjuvant therapy.

This analysis will be performed in the [name] and [name] Labs at Dana-Farber Cancer Institute.

9.2.5 Radiomics studies:

The baseline delta classification is based on the difference in iodine contrast measured in Hounsfield Units at the observed tumor/pancreas interface on the baseline (pre-treatment) CT scan, as previously described (60). The interface response is based on the change in the interface morphology, comparing the baseline and post-neoadjuvant therapy CT scan (61). These CT scans will be de-identified prior to analysis and linked to the patient through a unique identifier in the database for the study. The CT scans will be analyzed in the lab of [name] at MD Anderson Cancer Center and the radiomic measurements will be stored in the database for the study for subsequent correlations as proposed.

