11.1.6 Progression-Free Survival

Overall Survival: Overall Survival (OS) is defined as the time from randomization (or registration) to death due to any cause, or censored at date last known alive.

Progression-Free Survival: Progression-Free Survival (PFS) is defined as the time from randomization (or registration) to the earlier of progression or death due to any cause. Participants alive without disease progression are censored at date of last disease evaluation.

Time to Progression: Time to Progression (TTP) is defined as the time from randomization (or registration) to progression, or censored at date of last disease evaluation for those without progression reported.

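### Survival curves by CT interface response need a start date at the CT that defines it, and arm comparisons by radiomic feature should be limited to the baseline delta class (low priority, exploratory)

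*Combined protocol and SAP*

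**What the plan says.** Section 2.5 plans the radiomics work on two scans: "we plan to measure the baseline and post-neoadjuvant CT scans of patients as previously described". It then says that "Clinical outcomes will be correlated with the CT-based radiomic features and Kaplan Meier curves will be constructed", with univariable and multivariable analyses described only as appropriate.

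Section 9.2.5 defines the two features. Delta is a pre-treatment measurement: "The baseline delta classification is based on the difference in iodine contrast measured in Hounsfield Units". Interface response is a change: "The interface response is based on the change in the interface morphology, comparing the baseline and post-neoadjuvant therapy CT scan".

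On timing, section 5.3.2 says "There will be eight cycles of FOLFIRINOX, with each cycle being 14 days in length". Section 5.3.3 places restaging after cycles 4 and 8 and makes absence of progression on those scans the condition for going on to radiation or surgery. Calendar footnote k adds a scan before surgery, which for borderline patients follows chemoradiation.

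On the clock, section 11.1.6 says PFS "is defined as the time from randomization (or registration) to the earlier of progression or death due to any cause". Section 13.6 also starts PFS and OS at randomisation.

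On treatment effect, the radiomics background in section 2.1 hypothesises that "patients with high delta tumors and poor interface responses will exhibit differential responses to the experimental therapy", compared with low delta tumors.

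Section 13 contains no radiomics analysis. No landmark, time-dependent covariate or rule for patients without the second CT appears anywhere.

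**The concern.** A patient must reach the post-neoadjuvant CT before interface response can be scored. If the curves run from randomisation, three separate problems follow.

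1. Everyone with a score was alive, and largely event-free, up to the scan, so the early part of each curve is guaranteed and the curves overstate outcome.
2. If the restaging CT is the scan used, it can both supply the class and call progression. A patient may then be a poor responder and a PFS event on the same day.
3. Interface response may itself be changed by NIS793. Arms compared within poor responders are no longer groups formed by randomisation.

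At stake is what the trial reports about interface response as a prognostic feature, or as a marker of NIS793 benefit. The main efficacy result is not at stake.

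**Working it through.** The documents state no figure for this analysis, so there is none to reproduce. Progression rates, PFS medians and class splits below are assumptions.

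**When the feature is known.** 8 cycles × 14 days = 112 days = 16 weeks = 112/30.44 = 3.7 months from first dose. Section 5.3.3 allows the scan from the cycle 8 pump disconnect, about 7 × 14 + 2 = 100 days, so 16 weeks is nominal. If the pre-surgery scan is meant, it is later for borderline patients; 6.5 months is used below as an assumed value.

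**Height of the curves.** Take exponential PFS with median m and scan at time L, dropping patients with an event before L.
- Fraction lost: 1 − 2^(−L/m). At L = 3.7 months this is 19% for m = 12 and 7% for m = 36. At L = 6.5 it is 31% and 12%.
- Apparent 12-month PFS from randomisation: 2^(−(12 − L)/m).

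| m (months) | True 12-month PFS | Apparent, L = 3.7 | Apparent, L = 6.5 |
|---|---|---|---|
| 12 | 0.50 | 0.62 | 0.73 |
| 24 | 0.71 | 0.79 | 0.85 |
| 36 | 0.79 | 0.85 | 0.90 |

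**Good versus poor, unscanned patients dropped.** Both classes share the same guaranteed period. Simulated with 45 patients and a feature unrelated to PFS, the 5% log-rank test from randomisation rejects in 4.5-6.1% of trials across m = 12 to 36 and both scan times. Guaranteed time alone raises the curves without materially biasing this comparison.

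**Good versus poor, some patients progressing on the scan itself.** Settings: 45 patients, scan at 4 months, exponential post-scan PFS with a 12-month median, censoring uniform over 18-60 months, a random 50:50 class among non-progressors, and no association after the scan. Rejection rates over repeated runs, with 10% to 20% progressing on the scan:

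| Progressors classed poor | Log-rank from randomisation |
|---|---|
| All (worst case) | about 10% rising to 20-24% |
| 70% | 6-8% |
| Unrelated to progression (50%) | 5-6% |

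Starting at the scan among patients progression-free on it gives about 5-6%.

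**Arms compared within a post-randomisation class.** An illustrative simulation of 400,000 patients had no treatment effect on survival (median 17.5 months in both arms). A latent prognostic factor drove both survival and class, and the experimental arm shifted the share of good responders.

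| Good responders, A vs B | Median among poor, A vs B | Median among good, A vs B |
|---|---|---|
| 59% vs 50% | 12.7 vs 13.1 months | 22.2 vs 23.3 months |
| 71% vs 50% | 11.6 vs 13.3 months | 20.7 vs 23.3 months |

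The within-class differences are artefacts of conditioning. Their direction and size depend on the assumed model.

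**The case against.** The strongest reply is that this is a gap in specification rather than a chosen faulty analysis. Section 2.5 gives no time origin for these curves, and the analyses it calls appropriate could include a landmark. That is fair: randomisation is inferred because it is the only origin the documents define. It still leaves the analyst with no other written instruction.

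Several stronger readings are tempting, and the documents do not support them.
- A reader might take the 10-24% rejection rate as expected. It requires every progressor on the scan to be classed poor. Interface response is a change in morphology at the tumor edge, whereas RECIST progression (section 11.1.4) is growth in summed diameters or a new lesion. A new distant lesion is a PFS event whatever the interface shows.
- A reader might infer that guaranteed time by itself makes poor responders look worse. It does not if patients without a scan are dropped. It would if early events were classed as poor by default (10-26% rejection with the scan at 3.7 months), but nothing in the documents says that will happen.
- A reader might extend the circularity to OS. Progression on a scan is not a death, so the scan-date overlap concerns PFS only.
- A reader might think a predictive-marker test is planned. The differential-response wording is one background hypothesis whose comparator is low delta tumors. No arm-by-interface test appears in 2.5, 9.2.5 or 13, and objective 1.4.5 speaks of correlations.

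**Conclusion.** The point holds for interface response, at low priority. Curves from randomisation sit too high: under exponential PFS with a 12-month median, 12-month PFS would read 0.62-0.73 against a true 0.50, with less distortion at longer medians. The PFS comparison between classes ranges from essentially nominal (5-6%) to 10-24% in the worst case, depending on how far class overlaps with progression on the same scan, which the documents do not tell us. An arm comparison within interface classes would not be randomised.

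It would be too much to infer that objective 1.4.5 as a whole is compromised. Delta is measured before treatment, so both its curves from randomisation and its arm comparisons are sound on this point. Correlations with immune measures and pathological response use no survival clock. The primary MPR analysis, PFS and OS by arm, and safety are untouched.

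**What to change.** In sections 2.5 and 9.2.5:
- Name the CT that defines interface response in the resectable and in the borderline stratum.
- Start PFS and OS curves by interface response at the date of that CT, among patients alive then and, for PFS, also progression-free on it. Report how many patients have no such scan.
- Limit arm-by-feature analyses to the baseline delta class.
- Report interface response by arm as an outcome.

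This takes a few lines of text and no new scans, data or patients. The cost is that early progressors leave the PFS landmark set, which shrinks an already small sample of 45, and the resulting curves describe only patients who reach the scan.

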3. PARTICIPANT SELECTION

3.1 Eligibility Criteria

In order to be eligible for participation in this trial, the subject must:

- 3.1.1 The clinical, radiographic, and pathologic evidence support a diagnosis of pancreatic adenocarcinoma, with histology confirmatory for adenocarcinoma.
- 3.1.2 Subjects must be determined to meet the criteria for resectable or borderline resectable pancreatic cancer based on the M.D. Anderson Cancer Center (MDACC) and Alliance Intergroup Criteria classification at initial diagnosis (Table 1). Patients with locally advanced or metastatic disease are not eligible for this trial.

Table 1. Criteria for resectability of pancreatic cancer

Vessel	Resectable	Borderline resectable	Locally advanced (Not Eligible)
SMA	No extension; normal fat plane between the tumor and the artery	Interface between tumor and vessel measuring less than 180° of the circumference of the vessel wall	Encased (>180°)
Celiac axis	No extension	Interface between tumor and vessel measuring less than 180° of	Encased and no technical option for reconstruction usually

Vessel	Resectable	Borderline resectable	Locally advanced (Not Eligible)
Common hepatic artery		the circumference of the vessel wall	because of extension to the celiac axis/ splenic/left gastric junction or the celiac origin
		Reconstructable [§] , short-segment interface between tumor and vessel of any degree	
SMV/PV	Patent	Interface between tumor and vessel measuring 180° or greater of the circumference of the vessel wall, and/or reconstructable [§] occlusion	Occluded and no technical option for reconstruction

Referenced from: Varadhachary et al., 2006(6) and Katz et al, 2013 (8). SMA, superior mesenteric artery; SMV/PV, superior mesenteric vein/portal vein.

[§] Normal vein or artery proximal and distal to the site of suggested tumor-vessel involvement suitable for vascular reconstruction

3.1.3 In subjects requiring biliary decompression, biliary stent or drainage using percutaneous transhepatic cholangiogram (PTC) are allowed.

3.1.4 Participants must be ≥ 18 years of age at the time of enrollment.

3.1.5 Participants must have an ECOG performance status 0-1 (see Appendix A).

3.1.6 Participants must have adequate organ and marrow function as defined as:

- Absolute neutrophil count $\geq 1,500/\text{mcL}$
- Platelets $\geq 100,000/\text{mcL}$
- Total bilirubin $\leq 1.5 \times$ institutional upper limit of normal
- AST(SGOT)/ALT(SGPT) $\leq 2.5 \times$ institutional upper limit of normal
- Creatinine $\leq 1.5 \times$ institutional upper limit of normal

OR

- Creatinine clearance ≥ 60 mL/min/1.73 m² for participants with creatinine levels above $1.5 \times$ upper limit of normal. Creatinine clearance can be calculated per institutional standard.

3.1.7 Female subjects of childbearing potential should have a negative urine or serum pregnancy within 72 hours prior to receiving the first dose of study medication. If the urine test is positive or cannot be confirmed as negative, a serum pregnancy test will be required. Female subjects of childbearing potential should be willing to use 2 methods of birth control or be surgically sterile or abstain from heterosexual activity for the course of the study through 9 months after the last dose of study medication. Subjects of childbearing potential are those who have not been surgically sterilized or have not been free from menses for > 1 year.

3.1.8 Male subjects should agree to use an adequate method of contraception starting with the first dose of study therapy through 6 months after the last dose of study therapy.

3.1.9 Ability to understand and the willingness to sign a written informed consent document.

